2.3. Study treatments

Patients will be treated with CDX-3379 plus cetuximab until progressive disease, unacceptable toxicity, or other criteria for discontinuation of study treatment.

A cycle is defined as 21 days. The dose of CDX-3379 is 12 mg/kg, with the option to increase the dose to 15 mg/kg if tolerated, delivered via intravenous (IV) infusion over 60 minutes. CDX-3379 will be administered every 3 weeks (on Day 1 of each 21-day cycle).

Cetuximab will be dosed with an initial loading dose of 400 mg/m² on Day 1 over 2 hours, followed by weekly doses of 250 mg/m² over 60 minutes. Patients who were previously treated with cetuximab within three months of study enrollment and required dose reduction due to adverse events attributed solely to cetuximab (e.g., rash) may initiate cetuximab at the same dose as was last received in the prior regimen, with or without an initial loading dose, as clinically appropriate. Cetuximab will be administered on Days 1, 8, and 15 of each 21-day

CELLDEX CDX3379-04: STATISTICAL ANALYSIS PLAN

[figure not shown]
June 24, 2020

Page 4

[figure not shown]
cycle. On Day 1 of each cycle, cetuximab should be administered approximately one hour after the completion of CDX-3379 infusions (and after completion of PK sampling).

As a routine precaution, the investigative site's medical staff is to closely observe patients for the duration of the cetuximab and CDX-3379 infusions and for at least one hour after the end of the infusions.

Exhibit 1. Study schema

* If CDX-3379 is discontinued, the patient is considered to be discontinued from the study treatment.

CONFIDENTIAL

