7.1. Extent of exposure

Study drug exposure will be summarized for the all treated population. Summaries will be separated for CDX-3379 and cetuximab. Summaries will include the number of infusions per patient as well as cumulative dose received, relative dose intensity, and duration of treatment. These parameters are defined in Exhibit 7.

Exhibit 7. Study drug parameter definitions

	CDX-3379	Cetuximab
Dosing schedule per protocol	12 mg/kg every 3 weeks, with option to increase to 15 mg/kg	400 mg/m ² IV (loading dose) once, then 250 mg/m ² weekly
Dose	Dose (mg/kg) is defined as total dose administered (mg)/most recent weight (kg).	Dose (mg/m ²) is defined as total dose administered (mg)/most recent body surface area (BSA) (m ²).
Cumulative dose	Cumulative dose (mg/kg) is the sum of the doses administered to a patient.	Cumulative dose (mg/m ²) is the sum of the doses administered to a patient.
Dose intensity ^a	Cumulative dose / [(Last dose date - first dose date + 21)/7]	Cumulative dose - first dose / [(Last dose date - second dose date + 7)/7]
Relative dose intensity (%) ^b	(Dose intensity/4 mg/kg/wk)*100	(Dose intensity/250 mg/m ² /wk)*100
Duration of treatment (weeks)	(Last dose date - First dose date)/7	(Last dose date - First dose date)/7

a. Dose intensity reported in mg/kg/wk for CDX-3379 and mg/m²/week for cetuximab. Dose intensity for cetuximab starts at the second dose.

b. Relative dose intensity for cetuximab starts at the second dose.

Dose delays will be summarized as the number of patients with at least one delay, the number of doses delayed per patient, and the reason for the delay. [REDACTED]

[REDACTED]

[REDACTED]

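### CDX-3379 relative dose intensity is referenced to 12 mg/kg for every patient, so after an increase to 15 mg/kg it no longer measures dose received against dose intended

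*SAP*

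**What the plan says.** SAP Section 2.3 gives the regimen: "The dose of CDX-3379 is 12 mg/kg, with the option to increase the dose to 15 mg/kg if tolerated". It also fixes the interval: "A cycle is defined as 21 days". The dosing-schedule row of Exhibit 7 in Section 7.1 repeats the option: "12 mg/kg every 3 weeks, with option to increase to 15 mg/kg".

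Exhibit 7 then defines CDX-3379 dose intensity as "Cumulative dose / [(Last dose date - first dose date + 21)/7" (closing bracket omitted here), in mg/kg per week, and relative dose intensity as "Dose intensity/4 mg/kg/wk)*100". The exposure summaries for the all treated population include "cumulative dose received, relative dose intensity, and duration of treatment".

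No visible text gives a second divisor for patients raised to 15 mg/kg, labels the ratio as relative to the starting dose, or splits the summary by whether the dose was raised. Text after the dose-delay sentence in Section 7.1 is redacted, and the protocol's dosing section is not shown.

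**The concern.** Relative dose intensity is normally read as the share of the planned dose that a patient received. For a patient who stays at 12 mg/kg, the Exhibit 7 formula gives that. For a patient raised to 15 mg/kg, the numerator grows and the divisor does not, so the higher dose offsets delays, omissions and reductions, and the result can still be at or above 100%.

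A summary over all patients then combines ratios whose full-delivery values differ: 100% for patients never raised, and up to nearly 125% for patients raised. A mean or median near 100% could reflect complete delivery, or raised patients with substantial shortfalls. Among the visible exposure summaries, this is the only one that compares dose received with a planned dose, so the others cannot be used to recover that comparison.

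**Working it through.** **Inputs.** Starting dose 12 mg/kg, optional level 15 mg/kg, 21-day cycle (SAP 2.3 and Exhibit 7); dose-intensity formula and divisor of 4 mg/kg/wk (Exhibit 7). Assumption: the first dose is 12 mg/kg and all later doses are intended at 15 mg/kg. The visible text does not say when an increase may occur.

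**The plan's divisor.** 12 / 3 = 4 mg/kg/wk, which reproduces the stated figure. The raised level is 15 / 3 = 5 mg/kg/wk.

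**Ceilings, for time spent at 15 mg/kg.** Full delivery: 5 / 4 = 125%. A 20% shortfall: 0.8 × 5 = 4, and 4 / 4 = 100%.

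**Whole courses that start at 12 mg/kg, on schedule.** For k doses the intended total is 12 + 15(k − 1) over 3k weeks. With full delivery the reading is that total / 3k / 4. A reading of 100% needs only 4 × 3k = 12k mg/kg, so the hidden shortfall is 1 − 12k / intended total.

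| Doses | Intended (mg/kg) | Weeks | Reading at full delivery | Dose that reads 100% (mg/kg) | Hidden shortfall |
|---|---|---|---|---|---|
| 2 | 27 | 6 | 112.5% | 24 | 11.1% |
| 4 | 57 | 12 | 118.8% | 48 | 15.8% |
| 6 | 87 | 18 | 120.8% | 72 | 17.2% |
| 8 | 117 | 24 | 121.9% | 96 | 17.9% |
| 12 | 177 | 36 | 122.9% | 144 | 18.6% |

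If the increase comes at the third dose, the hidden shortfall is 7.7% for 3 doses (39 intended, 36 needed) and 17.2% for 12 doses (174 intended, 144 needed).

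**Delay.** Six doses, 12 then 5 × 15 = 87 mg/kg, with three weeks of delay after the increase, so 21 weeks in all. Exhibit 7 gives 87 / 21 / 4 = 103.6%. The dose intended over those 21 weeks is 12 + 6 × 15 = 102 mg/kg, and 87 / 102 = 85.3%.

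**Reduction.** Doses 12, 15, 15, 12, 12, 12 on schedule total 78 mg/kg. Exhibit 7 gives 78 / 18 / 4 = 108.3%. Against 87 mg/kg intended (raised level kept as reference), 78 / 87 = 89.7%.

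**Pooled summary, illustration only.** Suppose half the patients stay at 12 mg/kg with full delivery (100%) and half follow the delayed course above. The Exhibit 7 mean is (100 + 103.6) / 2 = 101.8%. Against intended dose it is (100 + 85.3) / 2 = 92.6%. The per-patient gap is 103.6 − 85.3 = 18.3 percentage points, so the mean shifts by 18.3 times the share raised: 1.8 points at 10%, 4.6 at 25%, 9.2 at 50%. These shares are assumptions.

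**The case against.** The strongest reply is that dividing by the starting-dose intensity is a legitimate convention, and that it is visible here: the divisor is printed in the same exhibit as the schedule, 15 mg/kg is called an option, and a value above 100% plainly means more than the 12 mg/kg schedule was given. Part of this stands. A ratio to the starting dose is a usable quantity, and the plan could keep it. But the SAP does not label it that way, and a reader of the results table will not have the formula beside it. The label also would not separate a raised patient with a shortfall from a patient at 12 mg/kg with full delivery when both read 100%.

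A reader might also infer that a raised patient reads 125% and can lose a full fifth unseen. Because dosing starts at 12 mg/kg, those are limits that a whole course approaches without reaching.

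A reader might further infer that the plan overstates the tolerability of the combination. The documents do not support that. SAP 7.1 also reports number of infusions, cumulative dose, and delays with reasons. Protocol 12.5.6 tabulates the reasons for treatment modifications, SAP 7.2 reports adverse events by severity and by relation to each drug, and SAP 4.2 provides by-patient listings. Nor do raised patients always pull the average up: one with a large enough shortfall lowers it. The redacted text might hold further exposure summaries and cannot be counted either way.

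**Conclusion.** The point holds for the exposure summary. For any patient raised to 15 mg/kg, the Exhibit 7 ratio exceeds the ratio of dose received to dose intended. On full delivery it can approach 125%. A shortfall of up to about a fifth still reads 100%: about 11% to 19% over 2 to 12 doses if the increase comes at the second dose, and less if it comes later. The timing of the increase is an assumption.

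The pooled figure therefore mixes two scales and can mask under-delivery in raised patients. By how much cannot be stated, because the number of raised patients is not given. The consequence stops there: response rate, duration of response, progression-free and overall survival do not use this ratio, and a conclusion that tolerability as a whole is overstated would go beyond the documents.

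**What to change.** In Exhibit 7, define CDX-3379 relative dose intensity as 100 × cumulative dose received / cumulative dose intended. Accumulate the intended dose over the same period as the present formula (first dose to last dose plus 21 days), at 12 mg/kg per 21 days before an increase and 15 mg/kg per 21 days from the increase onward. For this calculation only, keep the raised level as the reference after any later reduction, so that the reduction shows. This is a reporting convention and implies nothing about which dose a patient should receive.

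Report the result overall and separately for patients never raised and patients raised. Keep the present ratio, if wanted, only as a second line labelled as relative to the 12 mg/kg starting dose.

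The cost is one extra derived variable from dosing data already collected, plus SAP wording, which SAP Section 4.11 allows in a revised plan before database lock. Values for patients never raised do not change, since 12 mg/kg per 21 days is the present divisor. Values for raised patients will be somewhat lower.

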7.2. Adverse events

Adverse events will be coded by MedDRA and summarized by system organ class (SOC), high level term (HLT), and preferred term (PT), and worst National Cancer Institute Common Terminology Criteria for Adverse Events (NCI CTCAE version 5.0) grade per patient. If a

patient reports more than one AE that was coded to the same SOC, HLT, or PT, the patient will be counted only once for that specific SOC, HLT, or PT.

Investigators will assess the relationship of each adverse event to each study drug. The relationship of each adverse event to study drug will be categorized as unrelated or related. If attribution is missing, the event will be assumed to be related to study drug.

All AE tables and listings will summarize treatment-emergent adverse events (TEAEs) defined as adverse events with onset on or after the date or the first dose of study drug or onset prior to the first dose of study drug but with worsened severity post-treatment. AEs without a severity rating that are reported post-treatment will be considered treatment-emergent. Presentations will include all adverse events through the 30 days following the last dose date.

The following TEAEs will be presented by severity:

- Serious adverse events
- All adverse events
- Adverse events related to CDX-3379
- Adverse events related to cetuximab, and
- Adverse events leading to study discontinuation.

All adverse events will be listed with MedDRA coding, onset and resolution dates, duration, seriousness, severity, relationship, actions, and outcome.

7.3. Deaths

The number of patients who died will be summarized in a by-patient listing of deaths including death date, cause of death, and relationship to study treatment.

7.4. Vital signs

Vital signs (weight, blood pressure, pulse rate, temperature, and respiratory rate) are collected according to the schedule in Exhibit 4 and categorized according to time point label. Patients will be monitored during and after infusion of CDX-3379 and cetuximab with assessment of

vital signs within 30 minutes pre-infusion, at 30 minutes during the infusion, within 5 minutes post-infusion, and as clinically indicated during the 1-hour post-treatment observation period. When cetuximab is administered over two hours, vital signs should additionally be assessed at 60 minutes and 90 minutes during the infusion.

For each vital sign parameter, summary statistics on the analysis value and change from baseline will be calculated by time point within each scheduled assessment. Pre-infusion values will be presented for by-visit reporting in tables and figures.

7.5. Electrocardiogram

Electrocardiogram (ECG) is administered according to the schedule in Exhibit 4 to collect heart rate, PR interval, RR interval, QRS interval, QT interval, and QTcF both pre- and post-infusion.

For each ECG parameter, summary statistics on the analysis value and change from baseline will be calculated by time point within each scheduled assessment. Pre-infusion values will be presented for by-visit reporting in tables and figures. In addition, a by-visit shift table of pre- vs. post-infusion values will be presented.

7.6. Eastern Cooperative Oncology Group (ECOG) performance status

ECOG performance status will be assessed at Screening, on Day 1 of each cycle, and at EOT. Shift from baseline to worst post-baseline value will be presented. Further details on the ECOG assessment can be found in Appendix 10.2.

7.7. Clinical laboratory parameters

Laboratory tests are conducted according to the schedule in Exhibit 4. For each quantitative, laboratory parameter (Exhibit 8) and scheduled visit, summary statistics on the analysis value and the change from baseline will be calculated and presented in SI units. If multiple records are available for a parameter on the same date, the results will be averaged to calculate the analysis value for reporting. Select laboratory parameters will be graded based on NCI CTCAE v5.0, and the shift from baseline to worst post-baseline grade will be presented.

CELLDEX CDX3379-04: STATISTICAL ANALYSIS PLAN

June 24, 2020

Page 30

Liver function test (ALT, AST, total bilirubin, and alkaline phosphatase [ALP]) elevations will be presented in categories relative to the upper limit of normal to identify potential cases of drug-induced liver injury. An evaluation of drug-induced serious hepatotoxicity (eDISH) plot that includes all pairs of ALT and total bilirubin values at scheduled and unscheduled assessments will also be presented.

All clinically significant abnormalities in laboratory values will be presented in a data listing. Urinalysis results will not be summarized but will be provided in a data listing.

CONFIDENTIAL

Exhibit 8. Clinical laboratory parameters

Clinical chemistry	Hematology & differential panel	Coagulation panel	Urinalysis	Thyroid function
Sodium	Hemoglobin	Prothrombin time (PT)	Protein	Thyroid stimulating hormone (TSH)
Potassium	Hematocrit	Activated partial thromboplastin time (aPTT)	Glucose	Free T4
Chloride	Mean corpuscular volume (MCV)	International normalized ratio (INR)	Specific gravity	Free T3
Bicarbonate	Erythrocyte count (RBC)		Blood	
Glucose	Platelets			
Blood urea nitrogen	Leukocytes (WBC)			
Creatinine	Neutrophil bands			
Calcium	Absolute neutrophils			
Magnesium	Absolute lymphocytes			
Phosphate	Absolute monocytes			
Alkaline phosphatase (ALP)	Absolute eosinophils			
Alanine transaminase (ALT)				
Aspartate transaminase (AST)				
Total protein				
Albumin				
Lactate dehydrogenase				
Total bilirubin				
Uric acid				
Amylase				
Lipase				

Table created manually.

8. Biomarker analyses

DNA sequencing will be conducted on pre-treatment tumor samples to assess for mutations in cancer-related genes such as FAT1, NOTCH1, NOTCH2, NOTCH3, AKT/PI3K, phosphatase and tensin homolog (PTEN) and/or ErbB family members.

Blood samples for biomarker analyses will be collected pre-infusion of CDX-3379, immediately after infusion, 60 minutes post-infusion on Day 1 of each cycle, and prior to cetuximab dosing on Days 8 and 15 of Cycle 1.

Baseline biomarker data for the subgroups of interest (FAT1 or NOTCH or both) will be summarized descriptively and any correlation with efficacy endpoints will be investigated as described in Section 6.3. [REDACTED]

[REDACTED]

9. References

1. International Conference on Harmonization of Technical Requirements for Registration of Pharmaceuticals for Human Use. Statistical principles for clinical trials (E9). International Conference on Harmonization; 1998.
3. Meinert, C. Clinical Trials: Design, Conduct, and Analysis. New York: Oxford University Press, 1986.
4. SAS, Version 9.4, Cary NC: SAS Institute; 2013.

10. Appendices

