10.2.5.4 Rapid Notification of Adverse Events of Interest

In addition to serious adverse events, the following adverse events will be reported within 24 hours using the same rapid notification procedures that are used for serious adverse events, even if the nature of the adverse event is not deemed serious:

- Any overdose (defined as the accidental or intentional administration of any dose of a product that is considered both excessive and medically important).
- Any suspected transmission of an infectious agent via study treatment. An infectious agent is defined as any organism, virus, or infectious particle, pathogenic or nonpathogenic.
- Potential Drug-induced liver injury (DILI), defined as:
 - Alanine aminotransferase (ALT) or aspartate aminotransferase (AST) elevation > 3 times upper limit of normal (ULN)

AND

 - Total bilirubin > 2 times ULN, without initial findings of cholestasis (elevated serum alkaline phosphatase),

AND

 - No other immediately apparent possible causes of AT elevation and hyperbilirubinemia, including, but not limited to, viral hepatitis, pre-existing chronic or acute liver disease, or the administration of other drug(s) known to be hepatotoxic.

- Death due to disease progression occurring within 28 days of study treatment; however, these events should not be documented as AEs or SAEs. If there is any uncertainty about the cause of death, the event should be reported as a serious adverse event.
- If a female becomes, or is found to be, pregnant within 6 months of exposure to the study treatments (maternal exposure) or if a male has been exposed to the study treatments within 6 months prior to contraception (paternal exposure).
- Any follow-up to the above-referenced events, including outcome of pregnancy. Further follow-up of birth outcomes will be handled on a case-by-case basis. In the case of paternal exposure, the investigator must obtain permission from the patient's partner in order to conduct any follow-up or collect any information.

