10.2.5.5 Laboratory Safety Data

The following clinical laboratory tests will be performed at the study visits outlined in [Table 1](#).

Table 10: Clinical Laboratory Tests to be Performed During Study

Hematology:	Clinical Chemistry:	Urinalysis
Hemoglobin*	Sodium*	Protein
Hematocrit*	Potassium*	Glucose
Mean corpuscular volume (MCV)	Chloride*	Specific gravity
Erythrocyte count (RBC)	Bicarbonate*	Blood
Leukocytes (WBC)*	Glucose (nonfasting)	
Platelets*	Blood urea nitrogen (BUN)*	
Differential:*	Creatinine*	Microscopic examination will be performed if indicated
Neutrophils	Calcium*	
Lymphocytes	Magnesium*	
Monocytes	Phosphate	
Eosinophils	Alkaline phosphatase*	
Basophils	Alanine transaminase (ALT/SGPT)*	
	Aspartate transaminase (AST/SGOT)*	
Differential should be reported consistently throughout the study as either an absolute count (preferred) or as a percentage.	Total protein	
	Albumin	
	Lactate Dehydrogenase (LDH)	
	Total Bilirubin*	
	Uric acid	
	Amylase*	
	Lipase*	
Coagulation Panel		
Prothrombin time (PT)/		
Partial thromboplastin time (PTT)		
International normalized ratio (INR)		
The coagulation panel should be done at screening		

* On study treatment days, tests must be performed within 24 hours prior to dosing, and results must be reviewed prior to study treatment administration. For all other laboratory tests, results from the prior visit must be reviewed before the administration of study treatment. See Section 8.2 for guidance regarding dosing modifications/delays due to toxicity, including laboratory abnormalities.

Investigators must document their review of each laboratory report by signing or initialing and dating each report, as well as addressing the clinical significance and causality (for significant abnormalities). Clinically significant abnormal laboratory results should be repeated as soon as possible (preferably within 24 to 48 hours). Section 10.2.5.1 provides further guidance as to when abnormal laboratory results are to be reported as adverse events.

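### SAP 7.7 averages same-date laboratory results without exempting the worst-grade shift or the liver-category tables, so a recorded threshold crossing can drop out of them

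*SAP*

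**What the plan says.** SAP 7.7 begins with summary statistics by scheduled visit, computed on an analysis value and its change from baseline. It then gives the rule for duplicates: "If multiple records are available for a parameter on the same date, the results will be averaged to calculate the analysis value for reporting". The outputs that follow are:

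- CTCAE grading: "Select laboratory parameters will be graded based on NCI CTCAE v5.0, and the shift from baseline to worst post-baseline grade will be presented".
- Liver tests: for ALT, AST, total bilirubin and alkaline phosphatase, "elevations will be presented in categories relative to the upper limit of normal to identify potential cases of drug-induced liver injury".
- An eDISH "plot that includes all pairs of ALT and total bilirubin values at scheduled and unscheduled assessments will also be presented".
- A listing: "All clinically significant abnormalities in laboratory values will be presented in a data listing".

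The duplicate rule is not limited to any of these outputs, and no other rule says which record feeds the grades or the liver categories.

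Two protocol sections bear on this. Protocol 10.2.5.5 says "Clinically significant abnormal laboratory results should be repeated as soon as possible (preferably within 24 to 48 hours". Protocol 10.2.5.4 defines potential drug-induced liver injury for 24-hour notification by three joint conditions: "Alanine aminotransferase (ALT) or aspartate aminotransferase (AST) elevation > 3 times upper limit of normal (ULN"; "Total bilirubin > 2 times ULN, without initial findings of cholestasis (elevated serum alkaline phosphatase"; and no other immediately apparent cause. SAP 4.7 takes baseline as the last non-missing value before the first dose.

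**The concern.** Averaging suits a by-visit mean, where each patient should contribute one value per visit. It does not suit a table whose purpose is to show the extreme. SAP 7.7 promises the worst grade after baseline and a liver screen by multiples of ULN, yet its only rule for same-date records replaces them with their mean. A programmer who follows the section literally would grade and categorise means.

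Same-day pairs are plausible. The notes to Protocol Table 10 require ALT, AST, bilirubin and other marked tests within 24 hours before dosing, with results reviewed before treatment, and clinically significant abnormalities are to be repeated promptly. An abnormal pre-dose result could therefore be rechecked the same day. If the recheck is lower, the patient may be tabulated in a milder category than the worst result on file. The SAP reports extremes elsewhere: worst grade per patient for adverse events (7.2) and worst value after baseline for ECOG status (7.6).

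**Working it through.** The plan gives no figure on this point, so there is none to reproduce. The check is arithmetic on the rule.

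**Inputs.** The averaging rule (SAP 7.7). Thresholds T of 3 x ULN for ALT or AST and 2 x ULN for bilirubin (Protocol 10.2.5.4), used only as illustrations, because SAP 7.7 does not state the cut-points of its liver table. About 45 treated patients (SAP 4.9). The laboratory values below are invented examples.

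**Direction.** For same-date results x and y, (x + y)/2 is never above the larger and never below the smaller. For high-direction and low-direction toxicities alike, the averaged post-baseline value gives the same category as the worst record or a milder one.

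**When a crossing is lost.** With x above T, the mean is at or below T exactly when y ≤ 2T − x. So y must itself be below T, and no positive repeat can hide a first value of 2T or more.

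| Test | First value (x ULN) | Lost if repeat is at or below | Fall needed |
|---|---|---|---|
| ALT/AST, T = 3 | 3.3 | 6 − 3.3 = 2.7 | 18% |
| ALT/AST, T = 3 | 3.6 | 6 − 3.6 = 2.4 | 33% |
| ALT/AST, T = 3 | 4.5 | 6 − 4.5 = 1.5 | 67% |
| Bilirubin, T = 2 | 2.2 | 4 − 2.2 = 1.8 | 18% |
| Bilirubin, T = 2 | 2.4 | 4 − 2.4 = 1.6 | 33% |

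**Examples.** ALT 3.6 and 2.2: (3.6 + 2.2)/2 = 2.9, not above 3; the worst value, 3.6, is. Bilirubin 2.3 and 1.6: (2.3 + 1.6)/2 = 1.95, not above 2; the worst value, 2.3, is.

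**How often, given a same-day pair.** The documents give no within-day variability, so I assumed coefficients of variation (CV) of 5%, 10% and 20% and simulated 400,000 independent lognormal pairs for each setting, with T = 3 x ULN.

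| True level (x ULN) | At least one value above 3 (CV 5 / 10 / 20%) | Mean above 3 | Crossing lost |
|---|---|---|---|
| 2.7 | 3.5 / 27.0 / 50.6% | 0.2 / 7.3 / 24.8% | 3.3 / 19.7 / 25.8% |
| 3.0 | 75.1 / 75.1 / 75.1% | 50.8 / 51.4 / 52.9% | 24.3 / 23.6 / 22.3% |
| 3.3 | 99.9 / 97.1 / 90.0% | 99.7 / 91.8 / 77.1% | 0.3 / 5.4 / 12.9% |

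These are proportions of same-day pairs at that level, not of patients. The proportion of patients cannot be estimated, because the number of same-day pairs is not given.

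**Weight of one patient.** 1/45 = 2.2 percentage points in a table of all treated patients.

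**The case against.** The strongest reply is that the rule may not reach these tables at all. The analysis value is introduced for by-visit summary statistics, SAP 7.4 and 7.5 use the term only in that sense, and the grading and liver sentences do not use it. That reading is possible. The text does not state it, however: the rule is general, is said to be for reporting, and stands directly before the grading sentence. Two programmers could produce different tables from it.

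Other points stand in part:

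- **Timing.** The protocol prefers repeats within 24 to 48 hours. Repeats on a later date are not averaged.
- **Safeguards.** Site adverse event reports, the 24-hour liver notification and the listings do not depend on the averaged value, so a case would not vanish from the report. They do not correct the summary tables.
- **Noise.** At a true level of 2.7 x ULN, a single value above 3 reflects variability, and taking the worst record keeps it. That is a real trade-off, but a table described as the worst grade should show the worst recorded one.

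A reader might also infer more than the documents support:

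- **The eDISH plot is distorted.** It is specified to show all pairs, scheduled and unscheduled, which points to individual values.
- **Toxicity confirmed by the repeat is hidden.** Two values above a threshold average above it; a crossing is lost only when the repeat falls below.
- **Same-day duplicates arise mainly after abnormal results.** No frequency is given.
- **The shift is always understated.** If averaging also reached a duplicated baseline, it could make the baseline milder and enlarge the shift. Only the direction of the post-baseline value is established.

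**Conclusion.** The point holds as a gap in SAP 7.7. Read plainly, the averaging rule extends to the worst post-baseline grade and the ULN categories, where it can make the tabulated result milder than the worst recorded value and never worse. Whether the tables would actually be programmed that way is not settled by the text.

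The size is small. It needs two or more results for one parameter on one date and a repeat low enough to bring the mean back across a cut-point, which is likeliest when the first value lies just beyond it. The number of such cases is unknown. In a descriptive single-arm study of about 45 patients, even one would move a table row by 2.2 percentage points. Systematic understatement of laboratory toxicity is not shown.

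**What to change.** Add to SAP 7.7: *Same-date averaging applies only to by-visit summary statistics. Post-baseline CTCAE grades, worst-grade shifts and ULN categories use every individual scheduled and unscheduled result, taking the worst value on the date. The baseline value remains as defined in Section 4.7.*

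This needs no new data, and SAP 4.11 already allows a documented revision before database lock. The cost is that an isolated spurious result will count in the worst-grade and liver tables; where a same-day repeat did not reproduce it, a footnote drawn from the listing can say so.

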PR	partial response
PR interval	period from the beginning of the P wave until the beginning of the QRS complex
PT	preferred term
PTEN	phosphatase and tensin homolog
QRS interval	combination of the Q wave, R wave, and S wave
QT interval	period from the beginning of the QRS complex to the end of the T wave
QTc	corrected QT interval
RECIST	Response Evaluation Criteria in Solid Tumors
RR interval	time elapsed between two successive R waves
SAE	serious adverse event
SAP	statistical analysis plan
SCI	Statistics Collaborative, Inc.
SD	stable disease
SOC	system organ class
$t^{1/2}$	apparent elimination half-life
TEAE	treatment emergent adverse event
TdP	torsades de pointes
WHO	World Health Organization

Definitions

Adverse event	An adverse event (AE) is any reaction, side effect, or other untoward event, regardless of relationship to study drug, which occurs anytime during the study in a patient administered study treatment.
All treated population	All patients treated with CDX-3379
Response-evaluable population	All patients who have measurable disease at baseline and receive one full dose of both CDX-3379 and cetuximab and have post-baseline tumor response assessment or discontinue study prematurely for disease progression, symptomatic deterioration, or death.
Serious AE	An AE occurring at any dose that: results in death; is a life-threatening experience; requires inpatient hospitalization or prolongation of an existing hospitalization; results in a persistent or significant disability/incapacity; or is a congenital anomaly/birth defect in the offspring of a patient who received study drug.
Treatment-emergent AE	AEs with an onset time after the initial dose of study drug.

1. Introduction

This statistical analysis plan (SAP) is based on Celldex's Protocol CDX3379-04 Amendment 1 [A Phase 2, Multicenter, Open-label Study to Evaluate the Efficacy and Safety of CDX-3379 in Combination with Cetuximab in Patients with Advanced Head and Neck Squamous Cell Carcinoma], dated June 28, 2019. The SAP summarizes key aspects of the study to provide context for statistical methods and presents details of the planned statistical methods addressing the study aims. To the extent that analyses described in this SAP differ from those described in the protocol, the methods of the SAP prevail. Any deviations to the SAP will be documented in the final clinical study report. Pharmacokinetic (PK) data analyses will be addressed in a separate analysis plan.

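### SAP 7.7 pairs only ALT with total bilirubin in its eDISH plot and states no joint AST-and-bilirubin summary, although the protocol defines potential liver injury by ALT or AST

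*SAP*

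**What the plan says.** Protocol 10.2.5.4 lists potential drug-induced liver injury among the events that need notification within 24 hours, serious or not. The aminotransferase condition is "Alanine aminotransferase (ALT) or aspartate aminotransferase (AST) elevation > 3 times upper limit of normal (ULN"; the bilirubin condition is "Total bilirubin > 2 times ULN, without initial findings of cholestasis (elevated serum alkaline phosphatase". A third condition is that no other cause is immediately apparent. All three must hold.

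SAP 7.7 plans two liver displays. The first covers ALT, AST, total bilirubin and ALP, whose "elevations will be presented in categories relative to the upper limit of normal to identify potential cases of drug-induced liver injury". The second, introduced as an addition, is "An evaluation of drug-induced serious hepatotoxicity (eDISH) plot" containing "all pairs of ALT and total bilirubin values at scheduled and unscheduled assessments". The SAP gives no reference lines for the plot and no joint aminotransferase-and-bilirubin category for the first display.

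AST is available: Protocol 10.2.5.5, Table 10 includes "Aspartate transaminase (AST/SGOT" in the chemistry panel. The SAP's introduction settles precedence: "To the extent that analyses described in this SAP differ from those described in the protocol, the methods of the SAP prevail". The plot as written in the SAP is therefore the one that would be produced.

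**The concern.** The protocol's rule is a joint condition: a raised aminotransferase, of either kind, and raised bilirubin in the same patient. The only joint display the SAP states uses one of the two aminotransferases. A patient whose ALT stays at or below the limit while AST exceeds it can satisfy the protocol's limits and still not stand out on that plot.

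The ULN categories do not clearly fill the gap. If AST and bilirubin are counted separately, the counts do not show whether both elevations occurred in one patient. The adverse-event summaries in SAP 7.2 have no separate line for rapid-notification events, so a non-serious potential liver-injury case has no output of its own. Protocol section 11 provides no independent data monitoring committee and leaves safety review to the sponsor, which makes it useful for the display to match the sponsor's own definition.

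**Working it through.** The plan gives no figure to reproduce. The check compares two rules.

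**Inputs**
- Protocol limits (10.2.5.4): (ALT > 3 x ULN or AST > 3 x ULN) and total bilirubin > 2 x ULN.
- Plot (SAP 7.7): ALT against total bilirubin.
- Assumption: the plot flags a point when ALT > c and bilirubin > 2 x ULN. The SAP does not give c, so I take c = 3 x ULN from the protocol rule and then vary it. Values are taken from the same date.
- The cholestasis and other-cause conditions are set aside here; neither can be read from the plot's two axes.

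**Comparison at bilirubin > 2 x ULN, with c = 3 x ULN**

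| ALT | AST | Protocol limits met? | Flagged on the ALT plot? |
|---|---|---|---|
| > 3 x | any | yes | yes |
| <= 3 x | > 3 x | yes | no |
| <= 3 x | <= 3 x | no | no |

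The second row is the gap.

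**Example:** ALT 2 x, AST 4 x, bilirubin 2.5 x ULN.
- Protocol limits: 4 > 3 and 2.5 > 2, so both are met.
- ALT plot: 2 is not > 3, so the point is not flagged.
- With the larger of the two: max(2, 4) = 4 > 3 and 2.5 > 2, so it is flagged.

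The full protocol definition would also need no initial rise in ALP and no other apparent cause in this patient.

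**Range for c**
- c of 3 x ULN or higher: every case in the second row is unflagged.
- c below 3 x, for example 2 x ULN: second-row cases with ALT above 2 x are now flagged; those with ALT at or below 2 x, including the example, are not.

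A lower line narrows the gap without closing it. The documents contain nothing from which to estimate how many patients would fall in the second row.

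**The case against.** The strongest reply is that this is a supplementary figure in a single-arm estimation study. No endpoint, estimate or decision rule depends on it. The SAP attaches the purpose of identifying potential liver injury to the ULN-category display, which includes AST, and offers the plot in addition. A reader might infer that the plot is the display meant to find these patients, or that the category display excludes pairing. The SAP supports neither reading: it gives the plot no such role, and it is silent on joint categories.

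A reader might also infer that AST-driven cases would be missed, and put each at 1/45 = 2.2% of patients. The documents do not support that either. Potential liver injury by AST needs 24-hour notification. AST and total bilirubin are among the tests that Table 10 requires to be reviewed before dosing. SAP 7.7 lists clinically significant laboratory abnormalities, SAP 7.2 lists all adverse events, and SAP 4.2 provides by-patient listings.

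Two further objections concern the remedy. Even a plot with AST would not reproduce the full protocol rule, because it shows neither cholestasis nor other causes. And a list with fixed limits could pick up values allowed at entry: inclusion criterion 9 permits AST and ALT up to 5 x ULN with liver metastasis, and bilirubin up to 5 x ULN with Gilbert's disease.

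These objections set the weight of the point and shape the fix. They do not remove the mismatch: the one joint display the SAP states leaves out half of the protocol's aminotransferase condition.

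**Conclusion.** The point holds as a small, inexpensive improvement. The SAP's stated joint liver display is narrower than the protocol's definition, and no other stated output pairs AST with bilirubin. The consequence is limited to presentation: some patients who meet the protocol's aminotransferase and bilirubin limits would not be flagged on the plot, and their paired values would have to be reassembled from listings.

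The size depends on two things the documents do not give: the plot's reference lines, assumed here to be the protocol's 3 x and 2 x ULN, and how often AST is raised without ALT. It would be wrong to conclude that AST goes unanalysed or that liver-injury cases go undetected.

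**What to change.** In SAP 7.7:

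1. Keep the ALT plot and add an AST panel against total bilirubin/ULN, or plot the larger of ALT/ULN and AST/ULN.
2. State the reference lines.
3. Count and list patients with ALT or AST > 3 x ULN and total bilirubin > 2 x ULN, citing Protocol 10.2.5.4. Show ALP and baseline values beside each, so that cholestasis and elevations already allowed at entry are visible.

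This takes a few sentences in the SAP, one extra panel and one short listing. It needs no new data and changes nothing in patient management. The downside is a few more points to review, some of which will reflect liver metastasis or Gilbert's disease at baseline.
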